7.9.3 Other Observations Related to Safety

The C-SSRS Baseline/Screening will be administered at Screening and the Since-Last-Visit C-SSRS will be administered at all other time points. The C-SSRS was developed by researchers at Columbia University as a tool to help systematically assess suicidal ideation and behavior in subjects during participation in a clinical trial of centrally acting drugs. The C-SSRS is composed of 3 questions addressing suicidal behavior and 5 questions addressing suicidal ideation, with sub-questions assessing severity. The tool is administered via an interview with the subject. If possible, the same interviewer should be used throughout the study for the same subject. It takes approximately 10 minutes to complete the C-SSRS.

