6.2.3 Endpoints

The GAS, adapted for MDD, is being used in this study. As this is an adaptation of an existing instrument, the results will provide novel outcome data for the goal attainment literature. Therefore, secondary endpoint assessments with validated instruments will provide additional confirmation of the effectiveness of vortioxetine in treating MDD when current antidepressant treatment is not adequate.

The following outcome measures will be used for secondary and exploratory endpoints as they are frequently used to assess clinical response: PHQ-9, PDQ-D, Q-LES-Q, WHO-5, CGI-S, CGI-I, Company and Company Confidential Information

Measures have been taken regarding the methodology of this study to assess suicidal risk. The selection criteria exclude the participation of subjects at significant risk for suicide. Throughout the study, signs of suicidal risk will be assessed both by rating scale assessment (C-SSRS) and by investigator's clinical judgment. Subjects will be withdrawn from the study in case of such risk. Furthermore, subjects will be screened for the history of suicidal behavior.

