9.3.5 Final Visit or Early Termination

The Final Visit will be performed at Visit 7 (Week 12) or at Early Termination Visit. For all subjects receiving study drug, the investigator must complete the End of Study eCRF page. Procedures to be completed during Final Visit/Early Termination Visit are detailed in Appendix A.

For subjects who permanently discontinue study drug early, all Final Visit/Early Termination assessments detailed in Appendix A should be performed in close proximity to, or at the time of, study drug discontinuation.

At the End of Study Visit the Clinician and subject satisfaction with the antidepressant treatment will be collected. In addition, Clinician and subject satisfaction with the GAS approach as a method for establishing treatment goals, evaluating progress towards treatment goals, and improving communication between clinicians and patients will be collected.

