5.4 Safety Assessments

Safety and tolerability of vortioxetine will also be evaluated using the following general assessments:

- Adverse events (AEs).
- AEs leading to discontinuation.
- Weight.
- Columbia-Suicide Severity Rating Scale (C-SSRS).

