7.0 METHODS OF ANALYSIS AND PRESENTATION

7.1 General Principles

This is an open-label study with a single treatment regimen and all comparisons are made to the conditions prior to the subject being switched to vortioxetine.

Baseline values are defined as the last observed value before the first dose of study switch medication.

All statistical analyses will be conducted using SAS® Version 9.2, or higher.

All confidence intervals, statistical tests, and resulting P-values will be reported as 2-sided and will be assessed at $\alpha=0.05$ significance level unless otherwise stated. P-values will be rounded to 3 decimal places prior to assessment of statistical significance.

Means and medians will be presented to 1 more decimal place than the recorded data. The standard deviations (SDs) will be presented to 2 more decimal places than the recorded data. Confidence intervals about a parameter estimate will be presented using the same number of decimal places as the parameter estimate.

Where appropriate, variables will be summarized descriptively by study visit. For the categorical variables, the count and proportions of each possible value will be tabulated. The denominator for the proportion will be based on the number of subjects who provided non-missing responses for the categorical variable. For continuous variables, the numbers of subjects with non-missing values, mean, median, SD, minimum, and maximum values will be tabulated.

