7.1.2 Definition of Visit Window

The window definitions as stated will be applicable for all the summaries where study visit data is presented and where study visit data are compared with baseline data. The window conventions for safety and efficacy parameters are consecutive; that is, the lower or upper bound of the windows is the midpoint between 2 consecutive study visits.

One or more results for a parameter may be obtained in a visit window. In such an event, the result with the closest date to the scheduled visit date will be used. In the event of 2 observations within a given visit window being equidistant to the scheduled visit date, the later observation will be used.

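### Does SAP 7.9.3, by naming no C-SSRS table or listing, put the report on suicidality at risk?

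*SAP*

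**What the plan says.** SAP 5.4, like Protocol 5.3, names four safety assessments: adverse events, adverse events leading to discontinuation, weight and the C-SSRS. SAP 7.9.1 gives a list of adverse event tables and listings. SAP 7.9.2 gives weight and vital signs summaries by visit and at end of study, and for vital signs a count of subjects with any markedly abnormal post-Baseline value over all visits, with a listing. SAP 7.9.3 covers the origin, content, interviewer and duration of the C-SSRS and says that "the Since-Last-Visit C-SSRS will be administered at all other time points". It names no output, and nothing there is marked as redacted. Protocol 13.1.4 deals with adverse events only.

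The general rules are these. SAP 7.1: "Where appropriate, variables will be summarized descriptively by study visit", with proportions "based on the number of subjects who provided non-missing responses for the categorical variable". SAP 7.1.2: "The window conventions for safety and efficacy parameters are consecutive", bounds lie at midpoints between visits, and when a window holds several results "the result with the closest date to the scheduled visit date will be used"; equidistant results go to the later one.

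On withdrawal, Protocol 6.2.3 says of suicidal risk: "Subjects will be withdrawn from the study in case of such risk". Protocol 9.3.5 says, of subjects who stop drug before Week 12: "all Final Visit/Early Termination assessments detailed in Appendix A should be performed in close proximity to, or at the time of, study drug discontinuation". Protocol Appendix A puts Week 12 and Early Termination in one column, and that column includes the C-SSRS.

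**The concern.** Three of the four named safety assessments have defined outputs and the fourth has none. The protocol relies on that fourth one to watch for suicidal risk, in an open-label study without a data safety monitoring committee (Protocol 11.0). Two bad outcomes can be imagined.

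- No table is made, and a named assessment goes unreported.
- A programmer with no specific instruction applies the general rules. Early Termination records can fall between scheduled visits, and the closest-date rule then prefers the scheduled record. After Screening the form covers only the time since the last visit, so the dropped record is the only one for its interval and no other row of the table would recover it.

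At stake is whether the report's account of suicidality from the scale could omit a subject withdrawn for that very reason.

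**Working it through.** The documents state no figure on this point, so there is none to reproduce. The check has two parts: how often the window rule would bite if it applied, and whether the plan makes it apply.

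**Inputs.** Scheduled days from Protocol Appendix A: 1, 15 (±3), 29 (telephone), 43 (±5), 64 (telephone), 85 (±5). The C-SSRS is done on Days 1, 15, 43 and 85 or at Early Termination. Window and selection rules are from SAP 7.1.2.

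**Window cuts**, (d1 + d2)/2 for consecutive visits:

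- All visits: (1+15)/2 = 8; (15+29)/2 = 22; (29+43)/2 = 36; (43+64)/2 = 53.5; (64+85)/2 = 74.5.
- C-SSRS visits only: (1+15)/2 = 8; (15+43)/2 = 29; (43+85)/2 = 64.

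**Example.** Negative on Day 15, positive at Early Termination on Day 20. Both days lie in the Week 2 window under either set of cuts. The distances are |15−15| = 0 and |20−15| = 5, so the negative record is kept.

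**Days lost, Week 2 on Day 15 and Week 6 on Day 43.** The possible Early Termination days run from 16 to 84 without Day 43: 69 − 1 = 68.

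| Windows defined by | Lost in Week 2 window | Lost in Week 6 window | Total of 68 |
|---|---|---|---|
| All visits | Days 16–21 or 16–22: 6 or 7 | Days 44–53: 10 | 16 or 17 |
| C-SSRS visits | Days 16–28 or 16–29: 13 or 14 | Days 44–63 or 44–64: 20 or 21 | 33 to 35 |

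The ranges arise because the SAP does not assign a day that falls exactly on a cut. Terminations before Week 2 are left out of the count.

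**Visits off target.** A Week 2 visit is at most 3 days from Day 15 and a Week 6 visit at most 5 from Day 43. Days 19–21 (4 to 6 days from Day 15) and Days 49–53 (6 to 10 days from Day 43) are therefore lost for any in-tolerance visit: 3 + 5 = 8 days.

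**Does the plan make the rule apply?** The loss needs both of the following.

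1. *By-visit tabulation.* SAP 7.1 calls for this only where it is appropriate, and nothing says it is for the C-SSRS. For vital signs, where single abnormal values matter in the same way, SAP 7.9.2 adds an over-all-visits count and a listing. A C-SSRS output in that form uses every post-dose record and loses nothing.
2. *Placement of Early Termination records by date.* Protocol Appendix A and Protocol 9.3.5 treat Week 12 and Early Termination as one final visit. If the record is reported under that visit, or in an end-of-study row such as SAP 7.9.2 gives for weight, it is kept.

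A third condition is clinical: risk must emerge between visits. If the scale shows risk at a scheduled Week 2 or Week 6 visit, the positive record is the scheduled one. It could be displaced only by a later record in the same window that is as close to the target day or closer.

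**What else reports such an event?** Under Protocol 10.2.1.2, an investigator who learns of a possible adverse event through an instrument must follow it up, and any event identified goes through normal reporting. SAP 7.9.1 tabulates treatment-emergent events, serious events and events leading to discontinuation, and lists all adverse events. SAP 7.3 counts withdrawals by primary reason.

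**The case for a change.** The strongest case for a change is that the protocol leaves methodology to the SAP (Protocol 13.1) and the SAP leaves this scale blank. SAP 7.1.2 expressly covers safety parameters, works by date, and states no exception for Early Termination. Adverse event tables do not report the scale, and Protocol 10.2.1.2 says the outcome instruments are not a primary means of collecting adverse events. A layout settled late, in an open-label study, could be chosen with the results in view. Writing it down would cost one table and one listing.

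Much of this stands: the omission is real, the day counts are right, and naming the output would be tidier. It does not show that the plan as written drops records. The nominal-visit reading is open, not proven, but so is the date reading. Data handling is also governed by separate Handling Rules for Analysis Data, which SAP 7.2 requires to be final before database lock and which are not among the documents reviewed. They may or may not settle the point. As for choosing a layout late, the study has one arm and the safety data carry no statistical testing (Protocol 13.1.4). There is no treatment contrast to favour, and a listing of positive records would leave little room for selection.

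**Conclusion.** No change follows. SAP 7.9.3 lacks detail that an analyst reporting a named safety assessment would ordinarily supply: subjects in the Safety Analysis Set with any post-dose ideation or behavior, from all records, with a listing. SAP 7.9.2 already contains a model for that form.

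The lost-record scenario is a caution to the programmer and not a consequence of the plan. Its size, 16–17 or 33–35 of 68 days with visits on target and 8 days for any in-tolerance visits, is a property of the window rule. It says nothing about how many subjects would be affected, because the documents give neither the timing nor the number of such withdrawals.

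At worst, one scale would be reported incompletely. The safety conclusion would not turn on it, because the same events can reach the adverse event, serious adverse event and discontinuation outputs.

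This rests on two assumptions: that investigators report events the scale reveals, as the protocol requires, and that analysts do not put a Since-Last-Visit suicidality form through a one-record-per-window by-visit table as its only output.

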7.10 Interim Analysis

The responder rate based on GAS score ≥ 50 will be calculated. The conditional probability of a responder rate of less than 50% at 120 subjects will be assessed; that is, using the data /trend of 60 patients at the interim look, the probability of (responder rate $< 50\%$) at the end of study (i.e., 120 subjects) will be calculated.

In addition, the change in PHQ9 and PDQ will be evaluated for internal decision making.

The report to be prepared for the interim analysis should include the tables for the following: demographics, disposition, GAS Response percents, GAS change from baseline, PHQ-9, and PDQ-D.

The end of the study will be the date of the last safety follow-up visit of the last subject based either on the first 60 completed subjects or the final 120 completed subjects.

7.11 Changes in the Statistical Analysis Plan

To be identified.

Appendix A. Criteria for Identification of Markedly Abnormal Values for Vital Signs

Parameter	Unit	MAV Definition (a)
Systolic Arterial BP	mmHg	< 85 mmHg or >180 mmHg
Diastolic Arterial BP	mmHg	<50 mmHg or >110 mmHg
Pulse	beats per minute	<50 bpm or >120 bpm
Weight	kg	Change of $\geq 7\%$ body weight

BP=Blood pressure.

(a) MAV criteria are applied to postbaseline values and changes relative to Baseline values, as appropriate.
